8.2.3 Expectedness

The Principal Investigator will be responsible for determining whether an AE is expected or unexpected. An AE will be considered unexpected if the nature, severity, or frequency of the event is not consistent with the risk information previously described for the study agent.

8.3 Time Period and Frequency for Event Assessment and Follow-Up

The occurrence of an AE or SAE may come to the attention of study personnel during study visits and interviews of a study participant presenting for medical care, or upon review by the DSMB. All AEs including local and systemic reactions not meeting the criteria for SAEs will be captured on the appropriate CRF. Information to be collected includes event description, time of onset, clinician's assessment of severity, relationship to study product (assessed only by those with the training and authority to make a diagnosis), and time of resolution/stabilization of the event. All AEs occurring while on study must be documented appropriately regardless of relationship. All AEs will be followed to adequate resolution.

Any medical condition that is present at the time that the participant is screened will be considered as baseline and not reported as an AE. However, if the study participant's condition deteriorates at any time during the study, it will be recorded as an AE. UPs will be recorded in the data collection system throughout the study.

Changes in the severity of an AE will be documented to allow an assessment of the duration of the event at each level of severity to be performed. AEs characterized as intermittent require documentation of onset and duration of each episode.

The PI will record all reportable events with start dates occurring any time after informed consent is obtained until 7 (for non-serious AEs) or 30 days (for SAEs) after the last day of study participation. At each study visit, the investigator will inquire about the occurrence of AE/SAEs since the last visit. Events will be followed for outcome information until resolution or stabilization.

All unresolved adverse events should be followed by the investigator until the events are resolved, the subject is lost to follow-up, or the adverse event is otherwise explained. At the last scheduled visit, the investigator should instruct each subject to report any subsequent event(s) that the subject, or the subject's personal physician, believes might reasonably be related to participation in this study. The investigator should notify the study sponsor of any death or adverse event occurring at any time after a subject has discontinued or terminated study participation that may reasonably be related to this study. The sponsor should also be notified if the investigator should become aware of the development of cancer or of a congenital anomaly in a subsequently conceived offspring of a subject that has participated in this study.

CONFIDENTIAL

This material is the property of the NYU School of Medicine and Langone Medical Center. Do not disclose or use except as authorized in writing by the study sponsor
Interventional Template Version: 28 APR 2017

8.4 Reporting Procedures – Notifying the IRB

8.4.1 Adverse Event Reporting

All AEs will be recorded in AE CRFs by a member of the study team. AEs will be recorded within 3 business days of the study team being made aware of the AE. The relationship of the AE to the study interventions will be noted by the PI. AEs that are deemed definitely related or probably related to the study interventions will be reported to the IRB and the DSMB within 3 days of their designation as such. The DSMB will determine the need for an emergency meeting between the DSMB and the study team (see safety oversight below). AEs that are deemed unrelated or not likely related to the study interventions will be recorded on CRFs as described above and will be reviewed at quarterly DSMB safety review meetings, and at annual review by the IRB.

8.4.2 Serious Adverse Event Reporting

All SAEs will be recorded in SAE CRFs by a member of the study team. SAEs will be recorded within 3 business days of the study team being made aware of the SAE. The relationship of the SAE to the study interventions will be noted by the PI. SAEs that are both unexpected and deemed related to the study interventions will be reported to the IRB and the DSMB within 24 hours of the PI designation as such. The DSMB will determine the need for an emergency meeting between the DSMB and the study team (see safety oversight below) or whether these can be reviewed at quarterly meetings. SAEs that are deemed unrelated or not likely related to the study interventions will be recorded on CRFs, will be reported to IRB and DSMB within 3 days of their designation as such and will be reviewed at quarterly DSMB safety meetings.

8.4.3 Unanticipated Problem Reporting

Incidents or events that meet the OHRP criteria for UPs require the creation and completion of an UP report form. It is the site investigator's responsibility to report UPs to their IRB and notify the DSMB. The UP report will include the following information:

- Protocol identifying information: protocol title and number, PI's name, and the IRB project number;
- A detailed description of the event, incident, experience, or outcome;
- An explanation of the basis for determining that the event, incident, experience, or outcome represents an UP;
- A description of any changes to the protocol or other corrective actions that have been taken or are proposed in response to the UP.

To satisfy the requirement for prompt reporting, UPs will be reported using the following timeline:

- UPs that are SAEs will be reported to the IRB within 3 days the investigator becoming aware of the event.
- Any other UP will be reported to the IRB within 3 days of the investigator becoming aware of the problem.

8.4.4 Reporting of Pregnancy

If any pregnancy occurs in a study subject, the PI will be notified immediately and the IRB will be notified within 3 days of discovery of the pregnancy. No data regarding safety or efficacy of Mavyret in pregnant women are available. Standard of care medications utilized for heart transplant recipients have known contraindications in pregnancies therefore any pregnancies will need to be managed as per standard of care with the heart transplant team. Counseling of pregnant subjects with regard to the risks of continuing versus discontinuing Mavyret will occur with patients once counseling with regard to the contraindications of the standard of care transplant medications has occurred.

CONFIDENTIAL

This material is the property of the NYU School of Medicine and Langone Medical Center. Do not disclose or use except as authorized in writing by the study sponsor
Interventional Template Version: 28 APR 2017

8.5 Study Halting Rules

Further enrollment of study subjects will be halted under the following conditions:

- Any patient death occurs and is deemed related to the intervention
- Any SAE deemed related to acute HCV infection occurs
- Any SAE deemed related to Mavyret occurs

The PI will inform the IRB and the DSMB within 24 hours of any of these events. The DSMB and study team will convene an emergency meeting as described below. The DSMB will provide recommendations for proceeding with any further enrollment. Patients who are already enrolled and receiving Mavyret treatment will continue to receive treatment unless the DSMB determines that an alternate course of therapy should be pursued for already-enrolled subjects.

8.6 Safety Oversight

It is the responsibility of the Principal Investigator to oversee the safety of the study. This safety monitoring will include careful assessment and appropriate reporting of adverse events as noted above, as well as the construction and implementation of a site data and safety-monitoring plan. Medical monitoring will include a regular assessment of the number and type of serious adverse events.

Safety oversight will be under the direction of a DSMB. This DSMB committee for this study will be comprised of individuals with expertise in transplantation, hepatology, infectious diseases and the treatment of hepatitis C, and ethics. These individuals will be:

[name] – Expert in medical ethics

[name] – Transplant nephrologist

[name] – Cardiologist

[name] – Cardiologist

[name] – Hepatologist

[name] – Transplant infectious diseases

The DSMB Charter with specific outlines of DSMB roles and responsibilities is uploaded as a separate attachment in Research Navigator.

The DSMB will be notified of all AEs and SAEs as outlined above in 8.4.1 and 8.4.2. Regular meetings of the DSMB and the study team will occur on a quarterly basis to review non-emergent AEs and SAEs.

The minimum group required to constitute an adequate DSMB-study team meeting will be (either in person or by teleconference): at least 4 of the DSMB members listed above, the PI, and at least one co-investigator. At quarterly meetings the DSMB will evaluate cumulative participant safety data and make recommendations regarding the safe continuation of the study.

The DSMB and study team will meet on an emergency basis in the following instances:

- Any SAE occurs that is unexpected and deemed related to the study intervention
- Any unanticipated problem occurs that is both serious and deemed related to the study intervention
- Any treatment failure occurs or drug resistant HCV strain is identified, and a rescue plan with alternate therapy is required

Emergency meetings will occur within one business day of the above-described event occurring or being recognized. Any event that prompts an emergency DSMB-study team meeting will be reported to the IRB within 24 hours of the event occurring or being recognized.

9 Clinical Monitoring

CONFIDENTIAL

This material is the property of the NYU School of Medicine and Langone Medical Center. Do not disclose or use except as authorized in writing by the study sponsor
Interventional Template Version: 28 APR 2017

Clinical site monitoring is conducted to ensure that the rights and well-being of human subjects are protected, that the reported trial data are accurate, complete, and verifiable, and that the conduct of the trial is in compliance with the currently approved protocol/amendment(s), with GCP, and with applicable regulatory requirement(s).

10 Statistical Considerations

10.1 Statistical and Analytical Plans (SAP)

As this is a single-arm observational study, no SAP will apply.

10.2 Statistical Hypotheses

We hypothesize that 100% of patients who develop HCV viremia will achieve SVR after completing an 8-week course of Mavyret treatment.

10.3 Analysis Datasets

Subjects will be entered into a study subject dataset which includes de-identified information. This will include: donor and recipient demographic data, donor HCV NAT, serology, and genotyping information, and results of all recipient HCV NAT, serologic, and genotyping data obtained throughout the course of the study.

10.4 Description of Statistical Methods

Since the anticipated study population will be a small size, statistical analyses will be limited to descriptive statistics. For patients who develop post-transplant viremia we will be able to compare our HCV cure rates to those that are expected for patients who receive treatment with these agents for chronic HCV.

10.4.1 General Approach

The study design will be single arm, open label. Descriptive statistics will include:

Incidence HCV viremia post-transplant (percentage)

Time course of exposure to development of clinically detectable viremia in those who develop viremia (median time to viremia with standard deviations)

Incidence of sustained clearance of HCV (cure) after treatment of viremia (percentage)

Time course of clearance of viremia after treatment initiation (median time to clearance with standard deviations)

Incidence of treatment failure/treatment resistant strains of HCV (percentage)

Characterization of distribution of HCV genotypes in patients who develop viremia (percentages)

Comparison of treatment failure rates to expected treatment failure rates for the treatments used (p value for significance will be set at $p < 0.05$ and two-tailed t-test will be used)

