5.6 Total Number of Participants and Sites

20 patients are expected to be enrolled and transplanted. No sites outside of NYULMC will enroll patients.

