7.3.3 Intermediate Visits

For the schedules below, the following time-post-event designations will be used:

POW (Post-operative week) – refers to weeks following the transplant operation

PMW (Post-Mavyret treatment week) – refers to weeks following the initiation of Mavyret therapy

All patients post-transplant will enter the Surveillance Phase which will entail weekly screening for the development of HCV viremia post-transplant for 8 weeks. Time in the surveillance phase is measured in reference to the transplant itself, in POW. Patients who never develop HCV viremia during the Surveillance Phase will transition to the No Transmission schedule detailed below. Time in the No Transmission arm is measured in reference to the transplant itself, in POW.

Patients who develop detectable HCV viremia during the Surveillance Phase will immediately exit the Surveillance Phase and enter the Mavyret Treatment arm schedule as detailed below. Time in the Mayvret Treatment arm is measured in reference to the date that Mavyret treatment was initiated, in PMW.

SURVEILLANCE PHASE SCHEDULE OF EVENTS

POW1 (+/- 1 day)

- In person visit, record vital signs
- Record standard of care labs: hematology, biochemistry, coagulation
- Collect study labs: HCV NAT

POW2 (+/- 2 days)

- In person visit, record vital signs
- Record standard of care labs: hematology, biochemistry, coagulation
- Collect study labs: HCV NAT

POW3 (+/- 3 days)

- Record standard of care labs: hematology, biochemistry, coagulation
- Collect study labs: HCV NAT

POW4 (+/- 5 days)

- In person visit, record vital signs
- Record standard of care labs: hematology, biochemistry, coagulation, HBV serologies and NAT, HIV serologies
- Collect study labs: HCV NAT

CONFIDENTIAL

This material is the property of the NYU School of Medicine and Langone Medical Center. Do not disclose or use except as authorized in writing by the study sponsor

POW5 (+/- 5 days)

- Record standard of care labs: hematology, biochemistry, coagulation
- Collect study labs: HCV NAT

POW6 (+/- 5 days)

- Record standard of care labs: hematology, biochemistry, coagulation
- Collect study labs: HCV NAT

POW7 (+/- 5 days)

- Record standard of care labs: hematology, biochemistry, coagulation
- Collect study labs: HCV NAT

POW8 (+/- 5 days)

- Record vital signs
- Record standard of care labs: hematology, biochemistry, coagulation,
- Collect study labs: HCV NAT and serology

NO TRANSMISSION ARM SCHEDULE OF EVENTS

POW12 (+/- 7 days)

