10.5 Sample Size

10 patients are expected to enroll in this trial.

We expect that less approximately 70% of patients will develop evidence of HCV infection transmitted from the HCV-positive donor and will be treated for HCV infection. We expect that 100% of the patients who are treated for HCV infection will achieve SVR.

This is a single-arm study with no comparison group. The power to detect a difference in observed versus expected depends upon the true efficacy of the therapy. The reported efficacy of the therapy is 98%. With an estimated 7 patients who will be treated, a single treatment failure will be regarded as a significant deviation from the expected outcome.

11 Source Documents and Access to Source Data/Documents

Source data is all information, original records of clinical findings, observations, or other activities in a clinical trial necessary for the reconstruction and evaluation of the trial. Source data are contained in source documents. Examples of these original documents, and data records include: hospital records, clinical and office charts, laboratory notes, memoranda, subjects' diaries or evaluation checklists, pharmacy dispensing records, recorded data from automated instruments, copies or transcriptions certified after verification as being accurate and complete, microfiches, photographic negatives, microfilm or magnetic media, x-rays, subject files, and records kept at the pharmacy, at the laboratories, and at medico-technical departments involved in the clinical trial. It is acceptable to use CRFs as source documents. If this is the case, it should be stated in this section what data will be collected on CRFs and what data will be collected from other sources.

The study case report form (CRF) is the primary data collection instrument for the study. All data requested on the CRF must be recorded. All missing data must be explained. If a space on the CRF is left blank because the procedure was not done or the question was not asked, write "N/D". If the item is not applicable to the individual case, write "N/A". All entries should be printed legibly in black ink. If any entry error has been made, to correct such an error, draw a single straight line through the incorrect entry and enter the correct data above it. All such changes must be initialed and dated. DO NOT ERASE OR WHITE OUT ERRORS. For clarification of illegible or uncertain entries, print the clarification above the item, then initial and date it.

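### Time to viremia and time to clearance are summarised as a median with standard deviations; the spread should be given as interquartile range and range

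*Protocol*

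**What the plan says.** Protocol 10.4.1 lists the descriptive statistics. Onset of viremia, in patients who become viremic, is given as "median time to viremia with standard deviations". Clearance after the start of treatment is given as "median time to clearance with standard deviations". SAP 1.4.1 has the same two lines. Neither document names an interquartile range, a range, a confidence interval for the median or a time-to-event summary for these times.

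The two lines serve a secondary objective in Protocol 3.2, the time course of viremia and of its clearance. Protocol 10.4.9 adds that individual data on these kinetics will be evaluated.

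The times are read on a visit grid. Protocol 7.3.3 plans "weekly screening for the development of HCV viremia post-transplant for 8 weeks". The clearance clock is the post-Mavyret week, which "refers to weeks following the initiation of Mavyret therapy", with HCV NAT listed weekly from PMW1 to PMW12.

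On numbers, Protocol 10.5 says "10 patients are expected to enroll in this trial" and "With an estimated 7 patients who will be treated", while Protocol 5.6 says "20 patients are expected to be enrolled and transplanted".

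**The concern.** The median and the SD answer different questions. The SD is built from distances to the mean, and no mean is planned. A reader given a median and an SD learns neither how the times are spread around the median nor how precisely the median is known. This follows from the definition and needs no assumption about the shape of the data.

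Shape decides whether the mismatch does harm. Onset times cannot fall before the first draw. Under Protocol 10.4.3 any positive post-transplant NAT counts, with testing for at least 6 months, so a late first positive is possible. One such value among a handful moves the SD a great deal and the median hardly at all.

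Clearance has a further gap. A treated patient who never clears has no clearance time, and the plan does not say whether that patient is left out. If so, the median describes only those who clear.

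What is at stake is how readable the only summary statistics planned for the time-course objective will be.

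**Working it through.** **Step 1: how many times will be summarised.** Protocol 10.5 expects "approximately 70% of patients will develop evidence of HCV infection".
- With 10 patients: 10 × 0.70 = 7.0, which reproduces the plan's 7.
- With 20 patients (Protocol 5.4 and 5.6): 20 × 0.70 = 14.0, which does not match 7.

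The mismatch between median and SD is present at either size.

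**Step 2: what the SD measures.** SD = √[Σ(x − mean)² / (n − 1)]. The median does not appear in it.

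**Step 3: effect of one late value.** The documents give no distribution, so these onset weeks are assumed (n = 7, quartiles by linear interpolation).

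| Assumed weeks | Median | IQR | Range | Mean | SD |
|---|---|---|---|---|---|
| 1, 1, 1, 1, 2, 2, 2 | 1 | 1–2 | 1–2 | 1.43 | √(1.71/6) = 0.53 |
| 1, 1, 1, 1, 2, 2, 3 | 1 | 1–2 | 1–3 | 1.57 | √(3.71/6) = 0.79 |
| 1, 1, 1, 1, 2, 2, 8 | 1 | 1–2 | 1–8 | 2.29 | √(39.43/6) = 2.56 |
| 1, 1, 2, 2, 2, 3, 3 | 2 | 1.5–2.5 | 1–3 | 2.00 | √(4.00/6) = 0.82 |

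The first three rows differ in one patient only. Median and IQR are identical and the range shows the late value directly, while the SD grows almost fivefold (2.56 / 0.53 = 4.8). In the third row a reader who subtracts the SD from the median gets 1 − 2.56 = −1.56 weeks. In the symmetric fourth row the same subtraction gives 2 − 0.82 = 1.18 weeks, which misleads nobody.

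**Step 4: how much this depends on skew.** Samples of 7 onset times were simulated as log-normal with median 1.5 weeks, rounded up to whole weeks and limited to weeks 1 to 8 (100,000 samples per setting). The share in which median minus SD falls below week 1, the earliest value on the grid, was:
- log-SD 0.3: about 1%
- log-SD 0.6: about 42%
- log-SD 1.0: about 75%

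The harm runs from negligible to common, and the documents do not say where in that range the trial lies.

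**Step 5: patients who never clear (time to clearance only).** Protocol 10.5 cites 98% efficacy, so take a 2% failure rate.
- Chance of at least one failure among 7 treated: 1 − 0.98⁷ = 0.132.
- Among 14 treated: 1 − 0.98¹⁴ = 0.246.

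These are upper figures for non-clearance, since some failures may be relapse after clearance. If one of seven never clears, the median over all seven is the 4th ordered time, with that patient ranked last. The median over the six who clear is the midpoint of the 3rd and 4th. With assumed clearance weeks 1, 2, 2, 3, 4, 4 and one patient not cleared, these are 3 and 2.5 weeks. The shift is small, but the plan should say which is meant.

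**The case against.** The strongest reply is that this is a slip of wording with little consequence. An SD is a legitimate measure of dispersion, and neither document plans an interval formed as median plus or minus SD. The Protocol expects viremia to appear early (2.1), and with early, tightly grouped times the SD does no harm. The time course is an objective in Protocol 3.2 but is not among the secondary endpoints in 4.2.2. Protocol 10.4.9 already commits to looking at individual kinetics, which for about 7 patients say more than any summary. Most of this stands, and it limits the point to a small correction. It does not make the SD a companion to the median, and individual data do not repair the planned summary line.

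Some stronger readings are tempting and should be set aside:

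- **That the reported spread would be wrong, or would run below zero.** The negative value in Step 3 needs a late case and a subtraction that the plan does not propose.
- **That wide visit windows count against the SD.** Draws at POW5 (day 30 to 40) and POW6 (day 37 to 47) can be 47 − 30 = 17 days apart at worst. That blurs the median and IQR just as much. It is a reason to use actual draw dates, and no more.
- **That patients without an event distort both summaries.** Time to viremia is already restricted to patients who become viremic. The question arises for clearance only, where the plan expects every treated patient to achieve SVR, tabulates treatment failure separately, and would still have a defined median with one non-clearer in seven.

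It is also fair to say that a range cannot include a patient with no clearance time. The count of such patients therefore has to stand beside it.

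**Conclusion.** The mismatch is real and appears in both lines of both documents: a median is paired with a measure of spread about a mean that is not reported. That conclusion rests on definitions alone. The practical size rests on assumed skew. One late value among about 7 times can multiply the SD several-fold while median and IQR stay fixed, whereas with nearly symmetric times the effect is small. The documents do not support a claim that the published figures would be wrong.

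The count of 7 holds for 10 patients. The Protocol also states 20, which gives about 14; the two enrolment figures need reconciling, but the conclusion is the same under either.

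The impact is minor. The summaries are descriptive, and no test, sample size calculation or halting rule in Protocol 8.5 depends on them.

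**What to change.** In both lines of Protocol 10.4.1 and of SAP 1.4.1, replace the standard deviations with the interquartile range and the full range. State that times are calculated from actual draw dates, and present the summaries alongside the individual data already planned in Protocol 10.4.9.

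For time to clearance only, add a sentence: report the number of treated patients who never clear next to the summary, and keep them in the median as not cleared by last follow-up, so that the median is not limited to those who clear. The range then covers the observed clearance times. Since Protocol 7.6 provides for rescue therapy, the same sentence should define what last follow-up means for a patient who goes on to it.

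The cost is a wording change in two documents and that one definition. It needs no new visits, samples or patients, because all recipient NAT results are already part of the dataset in Protocol 10.3.

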In this pilot study we propose utilizing HCV positive donors for HCV negative patients on the waiting list for a heart transplant at NYU Langone. We will propose careful early post-transplant surveillance for the development of HCV viremia. We anticipate that approximately one-third of the patients will not develop viremia, despite the donor designation HCV positive. We anticipate that two-thirds of patients will develop early post-transplant HCV viremia. These patients will be immediately treated with an FDA-approved anti-HCV therapy which we expect will cure the HCV.

Willingness to participate in this trial will afford patients quicker access to heart transplantation, and will have the potential to reduce waitlist mortality.

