5.4 Strategies for Recruitment and Retention

Recruitment of patients will occur during routine evaluation visits to determine candidacy for a heart transplant at NYU Langone Health. Patients will be informed of the option to enroll in this study, and if interested, detailed information pertaining to the risks and benefits of the trial will be provided.

The signing of the acknowledgment to consider participation in the study will occur in the outpatient clinic. No additional information about potential candidates will be collected to determine interest or candidacy for this trial than would otherwise be normally collected as per standard of care for evaluation for a heart transplant.

Written informed consent for actual enrollment in the study will occur in the inpatient setting once a viable organ offer has been identified and the patient is admitted for potential transplantation.

The target sample size will be 20 patients.

CONFIDENTIAL

This material is the property of the NYU School of Medicine and Langone Medical Center. Do not disclose or use except as authorized in writing by the study sponsor
Interventional Template Version: 28 APR 2017

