10.4.3 Analysis of the Secondary Endpoint(s)

Secondary endpoint #1: 1-year patient survival rates in HCV negative heart recipients who receive a heart transplant from a HCV positive donor.

CONFIDENTIAL

This material is the property of the NYU School of Medicine and Langone Medical Center. Do not disclose or use except as authorized in writing by the study sponsor

Patients will have regular follow-up as standard of care for all heart transplant recipients. Patients survival will be readily apparent. Furthermore, all deaths of transplant recipients are required to be reported to UNOS.

Secondary endpoint #2: Incidence of HCV viremia among HCV negative recipients who receive a heart transplant from a HCV positive donor.

We will be measuring serial HCV NAT and serologic testing for a minimum of 6-months post-transplant. A patient will be considered to be viremic when a post-transplant HCV NAT test is positive. The incidence of viremia will be calculated as a percentage of the patients transplanted with a HCV-positive donor who develop HCV viremia by NAT testing.

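### No interval is planned for SVR, viremia incidence or 1-year survival, and the one planned test against the expected failure rate breaks down when there are no failures

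*Protocol*

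**What the plan says.** Protocol 10.4 limits the analysis to descriptive statistics because the study is small, then adds that "we will be able to compare our HCV cure rates to those that are expected" with these agents in chronic HCV. Protocol 10.4.1, repeated in SAP 1.4.1, gives the cure outcome as "Incidence of sustained clearance of HCV (cure) after treatment of viremia (percentage", where the bracket closes. The primary endpoint in Protocol 10.4.2 and SAP 1.4.2 is again a percentage. For viremia, Protocol 10.4.3 and SAP 1.4.3 say "The incidence of viremia will be calculated as a percentage of the patients transplanted with a HCV-positive donor". One-year survival is described as rates, with no estimator named. Neither document gives a confidence interval for any proportion.

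The last item of the 10.4.1 list compares treatment failure rates with expected failure rates by a two-tailed t-test at p < 0.05.

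Protocol 10.5 takes the reported efficacy as 98%, expects 100% SVR, estimates 7 treated patients, and says one failure among them will count as a significant departure from expectation. On enrolment, 10.5 says "10 patients are expected to enroll in this trial" and the Protocol Summary also says ten. Protocol 5.4 says "The target sample size will be 20 patients" and 5.6 says "20 patients are expected to be enrolled and transplanted".

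**The concern.** The plan sets out to compare an observed cure rate with a benchmark of about 98%. That comparison needs a measure of how far the observed rate could lie from the truth. With 7 treated patients the observed rate moves in steps of 1/7, or 14.3 points; with 14 treated, in steps of 7.1 points. Without an interval, 100% in 7 patients reads the same as 100% in several hundred.

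The t-test does not fill the gap. It treats 0/1 outcomes as roughly normal, and it has no usable form in the result the plan itself predicts. Following the plan exactly, the most likely report is a 100% figure with no valid statement of uncertainty, set beside 98%. The opposite error is also possible: Protocol 10.5 would call a single failure significant when it is not.

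**Working it through.** **Inputs.** Enrolment is 10 (Protocol 10.5, Protocol Summary) or 20 (Protocol 5.4, 5.6). The expected share treated is about 70% (Protocol 10.5: "We expect that less approximately 70% of patients will develop evidence of HCV infection transmitted from the HCV-positive donor") or two-thirds (Protocol 2.1: "We anticipate that two-thirds of patients will develop early post-transplant HCV viremia"). The benchmark SVR is 98%, so the benchmark failure rate is 2%. The documents name no confidence level; two-sided 95% is assumed here.

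**The plan's own figure.** 10 × 0.70 = 7.0, and 10 × 2/3 = 6.7. This reproduces the 7 treated in Protocol 10.5. With 20 enrolled, 20 × 0.70 = 14 (20 × 2/3 = 13.3).

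**Exact (Clopper-Pearson) intervals.** When all n succeed, the lower limit is 0.025^(1/n). For n = 7: 0.025^(1/7) = 0.590. For n = 14: 0.025^(1/14) = 0.768. Other counts use beta quantiles. The viremia and survival counts are illustrative.

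| Outcome | 10 enrolled | 20 enrolled |
|---|---|---|
| SVR, no failures | 7/7: 59.0% to 100% | 14/14: 76.8% to 100% |
| SVR, one failure | 6/7: 42.1% to 99.6% | 13/14: 66.1% to 99.8% |
| Viremia at 70% | 7/10: 34.8% to 93.3% | 14/20: 45.7% to 88.1% |
| Survival, no deaths | 10/10: 69.2% to 100% | 20/20: 83.2% to 100% |

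Sensitivity to method for 7/7: the Wilson lower limit is 64.6% and the one-sided 95% exact limit is 65.2%. For 14/14 they are 78.5% and 80.7%.

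**How well an all-success result separates true rates.** P(all succeed) = p^n.

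| True SVR | 7 of 7 | 14 of 14 |
|---|---|---|
| 98% | 86.8% | 75.4% |
| 90% | 47.8% | 22.9% |
| 80% | 21.0% | 4.4% |
| 70% | 8.2% | 0.7% |

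**The planned t-test.** I read it as a one-sample test of 0/1 failure values against 0.02.
- No failures: every value is 0, so the standard deviation is 0 and t = (0 − 0.02)/0 is undefined. The software used for this check returned minus infinity and p = 0, which taken literally would declare the failure rate significantly below 2%.
- One failure in 7: mean 0.1429, SD 0.378, standard error 0.378/√7 = 0.1429, t = (0.1429 − 0.02)/0.1429 = 0.86, df = 6, p = 0.42.
- One failure in 14: t = 0.72, p = 0.48.

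**The single-failure statement in Protocol 10.5.** At a true SVR of 98%, P(at least one failure in 7) = 1 − 0.98^7 = 13.2%. For 14 it is 1 − 0.98^14 = 24.6%. Both exceed 5%, and the 6/7 and 13/14 intervals both include 98%. The plan's own t-test (p = 0.42) also disagrees with 10.5.

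**The case against.** The strongest reply is that this is a descriptive pilot. The protocol says so, states that about 7 patients will be treated, and plans to evaluate individual participant data (10.4.9). It needs no power calculation, and no decision depends on an interval. Much of that stands: no power calculation is asked for here, and the documents do not hide how few patients are expected. But the plan goes beyond description by announcing a comparison with expected cure rates and a significance test, and an interval is itself a descriptive summary.

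Four stronger readings are tempting and are not supported:
- A reader might infer that only point percentages are planned. They are not: the same list in 10.4.1 names the t-test. The defect is that the test does not work here.
- A reader might infer that the plan would declare success on 100% SVR. No such rule exists. The stated rules react to failures: 10.5 treats one as a deviation, and 8.6 calls an emergency DSMB meeting for any treatment failure.
- A reader might take 59% as the figure. It holds for 7 treated and an exact two-sided 95% interval. Under the 20-patient sections the limit is about 77%.
- A reader might infer that survival is to be reported as a bare percentage. The documents say rates and leave the estimator open.

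**Conclusion.** The point holds in a limited form. The plan offers no valid measure of uncertainty for its comparison with 98% in the all-success case it expects. The exact lower limit for SVR is 59.0% with 7 treated and 76.8% with about 14; the alternative methods checked raise these to about 65% and 81% at most. All are far below 98%, so the conclusion does not depend on which enrolment figure is right, although the stated precision does. One failure in 7 is not a statistically significant departure from 98%. These results assume a treated share near 70% and a two-sided 95% level, which the documents do not fix for an interval. That a reader would over-read an unqualified 100% is a judgement, made reasonable by the comparison announced in Protocol 10.4. This is a weakness in analysis and reporting that should be corrected; it does not make the pilot design invalid.

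**What to change.** 1. In Protocol 10.4.1 to 10.4.3 and SAP 1.4.1 to 1.4.3, report SVR and viremia incidence as x/n with an exact (Clopper-Pearson) two-sided 95% interval. Do the same for 1-year survival where 12-month vital status is known for every recipient; if it is not, the plan must name another estimator with its interval.
2. Delete the two-tailed t-test. Base any statement against 98% on the exact interval, or on an exact binomial test.
3. Reword the single-failure sentence in Protocol 10.5 so that it makes no claim of statistical significance. The safety reporting and DSMB provisions triggered by a treatment failure are a separate matter and are not touched by this change.
4. Reconcile the 10 and 20 enrolment figures across the Protocol Summary, 5.4, 5.6 and 10.5. Then state the expected precision, for example 59.0% to 100% for 7/7 or 76.8% to 100% for 14/14.

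The cost is a few sentences of text, with no new data, patients or procedures. The downside is that the results will look less certain.
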